5.1.3 Statistical Methods for Observational Objective(s)

5.1.3.1 Hypotheses

No hypotheses will be tested. Descriptive statistics will be presented.

5.1.3.1.1 For Immunogenicity Observational Objective 1

hSBA GMT will be calculated and summarized at each time point. For GMT parameters, 95% CIs of point estimates will be calculated using normal approximation assuming they are log normally distributed. Reverse cumulative distribution curves (RCDCs) of hSBA titer will be provided.

Descriptive analyses on A, C, Y, and W serogroups on D0 and D30 using hSBA will include but not be limited to:

- GMT and 95% CI
- Titer distribution and RCDCs
- Percentage of subjects with titer $\geq 1:4$ and $\geq 1:8$ and 95% CI
- Percentage of subjects with titer ≥ 4 -fold rise from pre-vaccination to post-vaccination, and 95% CI

- Percentage of subjects with hSBA vaccine seroresponse^a

5.1.3.1.2 For Immunogenicity Observational Objective 2

rSBA GMT will be calculated and summarized at D0 and D30 after vaccination. For GMT parameters, 95% CIs of point estimates will be calculated using normal approximation assuming they are log normally distributed. RCDCs of rSBA titer will be provided.

Descriptive analyses on A, C, Y, and W serogroups on D0 and D30 using rSBA will include but not be limited to:

- GMT and 95% CI
- Titer distribution and RCDCs
- Percentage of subjects with titer $\geq 1:8$ and $\geq 1:128$ and 95% CI
- Percentage of subjects with titer ≥ 4 -fold rise from pre-vaccination to post-vaccination, and 95% CI
- Percentage of subjects with rSBA vaccine seroresponse^b

5.1.3.1.3 For Safety Observational Objective

Safety results in [Section 4.3.2.2](#) will be described for subjects in all study groups. The main parameters for the safety endpoints will be described by 95% CIs (Clopper-Pearson method) (6). Analyses will contain at least the descriptions listed in [Table 5.2](#).

^a hSBA vaccine seroresponse for serogroups A, C, Y, and W is defined as:

- For a subject with a pre-vaccination titer $< 1:8$, the post-vaccination titer must be $\geq 1:16$.
- For a subject with a pre-vaccination titer $\geq 1:8$, the post-vaccination titer must be at least 4-fold greater than the pre-vaccination titer.

^b rSBA vaccine seroresponse is defined as a post-vaccination titer $\geq 1:32$ for subjects with pre-vaccination rSBA titer $< 1:8$, or a post-vaccination titer ≥ 4 times the pre-vaccination titer for subjects with pre-vaccination rSBA titer $\geq 1:8$.

Table 5.2: Statistical analyses for safety observational objective

Safety Events	Time and Group	Description
Immediate unsolicited systemic AE	Within 30 minutes after injection for all subjects in Groups 1 and 2 at D0	Proportion of subjects that have the event, MedDRA terms, intensity, relationship to vaccine, study discontinuation
Solicited injection site reactions	Up to 7 days after D0 for all subjects in Groups 1 and 2	Proportion of subjects that have the event, onset, duration, intensity, action taken, study discontinuation, temperature collection routes(if applicable)
Solicited systemic reactions	Up to 7 days after D0 for all subjects in Groups 1 and 2	
Unsolicited AE	Up to 30 days after D0 for all subjects in Groups 1 and 2	Proportion of subjects that have the event, MedDRA terms, onset, duration, intensity, relationship, action taken, study discontinuation
SAE	Up to 6-month follow-up after D0 for all subjects in Groups 1 and 2	Proportion of subjects that have the event, MedDRA terms, onset, duration, relationship, seriousness criteria, outcome, study discontinuation
MAAE	Between Visit 1 and Visit 2 for all subjects in Groups 1 and 2 (as unsolicited AE) From Visit 2 to 6-month follow-up for all subjects in Groups 1 and 2	Proportion of subjects that have the event, MedDRA terms, onset, duration, intensity, relationship, action taken, study discontinuation

5.1.4 Complementary Output

Additional analyses by age group, gender and race will be provided in Appendix 15 of the CSR.

Immunogenicity analyses:

- hSBA GMTs and 95% CI – Per-Protocol Analysis Set
- Percentage of subjects with hSBA vaccine seroresponse^a and 95% CI – Per-Protocol Analysis Set

^a hSBA vaccine seroresponse for serogroups A, C, Y, and W is defined as:

- For a subject with a pre-vaccination titer < 1:8, the post-vaccination titer must be ≥ 1:16.
- For a subject with a pre-vaccination titer ≥ 1:8, the post-vaccination titer must be at least 4-fold greater than the pre-vaccination titer.

Safety analyses:

- Safety overview after injection –Safety Analysis Set

5.2 Analysis Sets

Three analysis sets will be used: the Full Analysis Set (FAS), the Per-Protocol Analysis Sets (PPAS) and the Safety Analysis Set (SafAS).

5.2.1 Full Analysis Set

The FAS is defined as the subset of subjects who received at least one dose of the study vaccine and had a valid post-vaccination serology result. All subjects will be analyzed according to the treatment group to which they were randomized.

5.2.2 Per-Protocol Analysis Set

The PPAS is a subset of the FAS. The subjects presenting with at least 1 of the following relevant protocol deviations will be excluded from the PPAS:

- Subject did not meet all protocol-specified inclusion criteria or met at least one of the protocol-specified exclusion criteria
- Subject did not receive vaccine
- Subject received a vaccine other than the one that he / she was randomized to receive
- Preparation and / or administration of vaccine was not done as per-protocol
- Subject did not provide post-dose serology sample in the specified time window or a post-dose serology sample was not drawn. Time windows will be defined as D30 to D44 (D30 +14 days) post vaccination.
- Subject received a protocol-prohibited Category 2 or Category 3 therapy / medication / vaccine
- Subject's serology sample did not produce a valid test result
- Subject had other protocol violations that affected the subject's immune response, as determined by the clinical team before locking the database.

5.2.3 Safety Analysis Set

The SafAS is defined as those subjects who have received at least 1 dose of the study vaccine and have any safety data available. All subjects will have their safety analyzed according to the vaccine they actually received.

If the vaccine received by a subject does not correspond to any study group, the subject will be excluded from the SafAS. The corresponding safety data will be presented in separate listings.

5.2.4 Other Analysis Set

rSBA subset

Subjects who received the vaccine and provided a valid post-vaccination rSBA result.

5.2.5 Populations Used in Analyses

All immunogenicity analyses will be performed on the PPAS. Additional immunogenicity analyses will be performed for exploratory purposes on the FAS. In the FAS, subjects will be analyzed by the vaccine group to which they were randomized.

All safety analyses will be performed on the SafAS. Subjects will be analyzed according to the vaccine they actually received.

5.3 Handling of Missing Data and Outliers

5.3.1 Safety

No replacement will be done. In all subject listings, partial and missing data will be clearly indicated as missing.

5.3.1.1 Immediate

For unsolicited non-serious systemic AEs, a missing response to the “Immediate” field is assumed to have occurred after the 30-minute surveillance period and will not be imputed.

For SAEs, missing or partially missing elapsed time from last vaccination recorded if within 24 hours will be assumed to have occurred after the 30-minute surveillance period and will not be imputed. Such SAEs will not be considered as immediate.

5.3.1.2 Causality

Missing causality (relationship) for unsolicited non-serious AEs and SAEs will be considered at the time of analysis as related to vaccination.

5.3.1.3 Measurements

Partially missing temperatures will be handled as described in [Section 4.4.2.1.1](#).

5.3.1.4 Intensity

For solicited reactions, missing intensities will be handled as described in [Section 4.4.2.1.1](#). For unsolicited non-serious AEs, missing intensities will remain missing and will not be imputed.

5.3.1.5 Start Date and Stop Date

Missing or partially missing start dates for unsolicited AEs will remain missing and not be imputed. If either the start or stop date is missing or partially missing, the time of onset will be considered to be missing. Nevertheless unsolicited AEs with missing time of onset will be included in analyses according to the visit collected.

Missing or partially missing stop dates for AEs (solicited reactions and unsolicited AEs) will remain missing and not be imputed.

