4.3.2.3.3 Unsolicited Non-serious Adverse Events From Day 0 to Visit 2 After Vaccination

In addition to recording solicited reactions, subjects will be instructed to record any other medical events that may occur between Visit 1 and Visit 2 after vaccination. Space will be provided in the DC for this purpose.

For each unsolicited non-serious AE, the following information is to be recorded:

- Start and stop dates^a
- Intensity of the event:
 - For measurable unsolicited non-serious AEs that are part of the list of solicited reactions, the size of the AE as well as the temperature for fever will be collected and analyzed based on the corresponding scale used for solicited reactions (see [Table 4.1](#) and [Table 4.2](#)).
 - Other unsolicited non-serious AEs will be classified according to the following intensity scale:
 - Grade 1: No interference with activity
 - Grade 2: Some interference with activity
 - Grade 3: Significant; prevents daily activity
- Action taken for each AE, if any (e.g., medication)

The action taken by the subject to treat any **unsolicited AEs** will be classified in the CRF using the following scale:

- 0: None
- 1: Medication (self-medication with an existing prescription or over-the-counter medication)
- 2: Health care provider contact (no new medication prescribed)
- 3: Health care provider contact and prescription of a new medication (health care provider instructed subject to take a new medication, either an over-the-counter medication or one requiring a written prescription)

^a The stop date of all related AEs will be actively solicited. For other events, the investigator will provide the stop date when it becomes available. AEs for which no stop date was obtained during the course of the trial will be considered as ongoing at the end of the trial.

- Whether the AE led to discontinuation
- Whether the AE was related to vaccination (for unsolicited systemic AEs)

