4.4.2.2.3 Last Vaccination

Last vaccination before any unsolicited non-serious AE is the study vaccination at V01.

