4.4.2.2.4 Time of Onset

Time of onset is derived from the start date of the unsolicited non-serious AE provided in the clinical database and the date of last vaccination:

- start date of the unsolicited non-serious AE – date of previous vaccination

The time of onset should be considered as missing only if one or both of the dates are missing or partially missing.

The unsolicited non-serious AEs will be analyzed "Within 30 days", which corresponds to AEs with a time of onset between 0 and 30 days after vaccination or missing. An AE with missing time

of onset will be considered to have occurred just after the vaccination indicated by the visit number, so will be included in these tables.

Note: Unsolicited non-serious AEs that occurred before vaccination (negative time of onset) or with a time of onset higher than defined above will not be included in analysis, but will be listed separately.

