4.4.2.2.5 Duration

Duration is derived from the start and stop dates of the unsolicited non-serious AE provided in the clinical database:

- stop date of unsolicited non-serious AE - start date of unsolicited non-serious AE + 1.

The duration should be considered as missing only if one or both of the start and stop dates of the unsolicited non-serious AE is missing or partially missing.

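### SAP 5.3.1.5 makes an adverse event's time of onset missing when only its stop date is missing, which contradicts the onset derivation in SAP 4.4.2.2.4

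*SAP*

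**What the plan says.** SAP 4.4.2.2.4 (Time of Onset) subtracts the vaccination date from the start date of the unsolicited non-serious AE. On missing values it says: "The time of onset should be considered as missing only if one or both of the dates are missing or partially missing". In that sentence the dates are the start date and the vaccination date. The same section defines the 30-day analysis window, "which corresponds to AEs with a time of onset between 0 and 30 days after vaccination or missing", and its Note says that "AEs that occurred before vaccination (negative time of onset) or with a time of onset higher than defined above will not be included"; those events are listed separately.

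SAP 5.3.1.5 (Start Date and Stop Date) gives a different rule: "If either the start or stop date is missing or partially missing, the time of onset will be considered to be missing". It continues: "Nevertheless unsolicited AEs with missing time of onset will be included in analyses according to the visit collected". It also says that missing stop dates are not imputed.

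Three other sections bear on the point:

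- SAP 4.4.2.2.5 makes duration missing "only if one or both of the start and stop dates of the unsolicited non-serious AE is missing or partially missing".
- SAP 4.4.2.2.3 confirms a single reference vaccination: "Last vaccination before any unsolicited non-serious AE is the study vaccination at V01".
- The footnote in SAP 4.3.2.3.3 says: "The stop date of all related AEs will be actively solicited". For other events the investigator supplies the date when it becomes available, and events with no stop date by the end of the trial are treated as ongoing.

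**The concern.** The two sections give different answers for the same record: an AE with a complete start date and an absent or partial stop date. The word 'only' in 4.4.2.2.4 rules out reading 5.3.1.5 as an extra condition. The SAP foresees such records, because it says how to treat AEs whose stop date was never obtained.

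Two outputs depend on which rule is used. The first is time to onset, a stated endpoint for unsolicited AEs (SAP 4.3.2.2) and a listed output in SAP Table 5.2. The second is the within-30-days table, which takes in every AE with missing onset. Two programmers working from different sections would report different onset summaries, and could report different 30-day counts, from the same data.

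**Working it through.** The plan gives no figure to reproduce, so the check applies both rules to the same example records.

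Inputs:

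- Onset formula, 30-day window and exclusion Note: SAP 4.4.2.2.4.
- Rule that also depends on the stop date: SAP 5.3.1.5.
- Collection of unsolicited AEs from Visit 1 to Visit 2: SAP 3.2 and 4.3.2.3.3.
- Visit 2 scheduled 30 to 44 days after vaccination: SAP 3.2.
- One vaccination only: SAP 4.4.2.2.3.

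| Example AE | Under 4.4.2.2.4 | Under 5.3.1.5 |
|---|---|---|
| Start D10, no stop date | Onset 10; in the 30-day table | Onset missing; still in the table, onset day lost |
| Start D35, Visit 2 later than D35, no stop date | Onset 35; left out and listed separately | Onset missing; counted within 30 days |
| Start before vaccination, no stop date | Negative onset; left out and listed separately | Onset missing; counted within 30 days |
| Start and stop dates complete | Onset known | Same |
| Start date missing | Onset missing | Same |

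Assigning an AE by the visit at which it was collected does not rescue the second and third rows. There is one vaccination, and 4.4.2.2.4 already places missing onset in the 30-day window.

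Illustration of size. Take non-serious AEs without a stop date and with onset on days 0 to V, where V is the day of Visit 2. The share wrongly placed in the 30-day table is the weight on days 31 to V divided by the weight on days 0 to V. The documents give no onset distribution, so the weights are assumptions.

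- Uniform onset, (V − 30)/(V + 1): V = 30 gives 0/31 = 0%; V = 37 gives 7/38 = 18%; V = 44 gives 14/45 = 31%.
- Front-loaded onset with half-life h days, weight r^day with r = 0.5^(1/h). The share is r^31 × (1 − r^(V−30)) / (1 − r^(V+1)).
  - h = 14: V = 30 gives 0; V = 37 gives 0.2155 × 0.2929 / 0.8476 = 0.0745 (7%); V = 44 gives 0.2155 × 0.5 / 0.8923 = 0.1208 (12%).
  - h = 7: V = 30 gives 0; V = 37 gives 0.0464 × 0.5 / 0.9768 = 0.0238 (2%); V = 44 gives 0.0464 × 0.75 / 0.9884 = 0.0352 (4%).

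These are shares of the AEs that lack a stop date, not of all AEs. AEs with onset on D0 to D30 stay in the table under either rule and lose only the onset day.

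**The case against.** The strongest reply is that the intended reading is obvious. Section 4.4.2.2.4 sits in the chapter on derivations and gives the only formula, and the stop date is not in it. The sections on serious AEs (4.4.2.3.2) and medically attended AEs (4.4.2.4) use the same methods, and nothing sends a programmer to 5.3.1.5 to compute onset. A statistical data review before database lock is also planned (SAP 5.6). This supports treating 5.3.1.5 as a drafting slip. It does not remove the contradiction: both texts are current, and no section in the supplied text says which prevails.

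The second reply is that the reach is narrow, and this stands. A misplaced AE must be non-serious, lack a complete stop date, and have begun after Day 30 or before vaccination; 5.3.1.5 must also have been followed. Stop dates of related AEs are actively sought, and related AEs that persist at the end of the trial are followed up (SAP 4.3.2.3.7), so the affected events would mostly be those judged unrelated. Onset before vaccination should be rare, because recording starts at Visit 1 and a pre-existing condition is not an AE unless it worsens or its clinical significance changes (SAP 4.3.2.1). The slip adds events to the 30-day table and removes none. The rule is the same in both groups, and no differential bias is shown.

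Third, the percentages are shares of an unknown number that may be zero, and the scenarios are not bounds, since late-onset AEs may be more or less likely to lack a stop date. The 31% figure needs both uniform onset and Visit 2 on the last scheduled day. That is also correct, so the figures show direction and mechanism only.

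**Conclusion.** The contradiction is real, and SAP 5.3.1.5 is wrong as written. Followed literally, it discards known onset days for a stated endpoint. It also moves AEs known to have begun on D31 to D44, or before vaccination, into a table from which 4.4.2.2.4 excludes them.

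The overall effect cannot be quantified, because the number of AEs without a stop date is not derivable from the documents. The illustrative 0% to 31% depends on 5.3.1.5 being followed and on the assumed onset patterns. No figure is claimed for serious AEs or for medically attended AEs collected after Visit 2.

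The consequences are confined to descriptive safety outputs on which no hypothesis is tested. The primary immunogenicity analysis and the onset of solicited reactions, which comes from daily diary intensities, are unaffected. The point should be fixed because the error is certain and the correction is very cheap, even though its likely effect is limited.

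**What to change.** In SAP 5.3.1.5, make time of onset missing when the start date or the vaccination date is missing or partial, in place of the start or stop date. Add that a missing or partial stop date affects duration only (4.4.2.2.5), and cross-refer to 4.4.2.2.4 for the onset derivation. Nothing further is needed for serious or medically attended AEs, since 4.4.2.3.2 and 4.4.2.4 already adopt that method.

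The cost is one phrase and one cross-reference in the SAP, with no new data and no added programming.

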5.3.2 Immunogenicity

Missing data will not be imputed. No test or search for outliers will be performed.

In order to appropriately manage extreme values (undetectable responses $< \text{LLOQ}$ and $\geq \text{ULOQ}$), the following computational rule is applied to the values provided in the clinical database for each blood sample drawn for analysis purposes:

- If a value is $< \text{LLOQ}$, then use the computed value $\text{LLOQ}/2$
- If a value is between $\geq \text{LLOQ}$ and $< \text{ULOQ}$, then use the value
- If a value is $\geq \text{ULOQ}$, then use the computed value ULOQ

The derived endpoint of fold-rise is computed for extreme values, to minimize the numerator and maximizes the denominator as in [Section 4.4.1.3](#).

5.3.3 Efficacy

Not applicable

5.4 Interim / Preliminary Analysis

No interim or preliminary analyses are planned.

5.5 Determination of Sample Size and Power Calculation

5.5.1 Calculation of Sample Size

A total of 900 subjects will be enrolled.

5.5.2 Power Calculations for the Primary Objective

[REDACTED]

[REDACTED]

[REDACTED]

5.6 Data Review for Statistical Purposes

Review of the data has been anticipated through the data review process led by data management before database lock. This review of the data will include a statistical review.

